4.2 Rationale for Trial Design

Rationale for Intervention Model

The comparison of the 2 groups (operated/non-operated) are chosen, because this gives an instant possibility to compare the knee functionality with and without surgical treatment.

Rationale for Duration

Only after 2 years the result can be evaluated. Biological processes in the meniscus are slow. Shrinkage of the transplant as described for CMI can occur later (up to 2 years). But normally after 2 years the remodelling process is finished. For this reason, close follow-up is performed for up to 2 years.

Rationale for Endpoints

The endpoints are the knee functionality after 2 and 5 years, the safety of the patient and the efficacy of the method. If the benefit-risk balance changes the investigator evaluates if the study will be continued.

Progression of osteoarthritis up to TKA are additional end points for single participants.

Interim Analysis

An interim analysis will be performed in 2 years. If the benefit-risk balance changes or the safety of the patient or the efficacy of the procedure is not any more given, the study will be stopped.

4.2.1 Rationale for Comparator

There is no comparator, the control group is the group of non-operated patients

4.2.2 Rationale for Adaptive or Novel Trial Design

There are no adaptive or novel trial design

4.2.3 Other Trial Design Considerations

There are no other trial design considerations.

4.3 Access to Trial Intervention After End of Trial

If the trial shows benefit for the patient the procedure will be performed after the trial as standard procedure by the investigator.

4.4 Start of Trial and End of Trial

The start date of the trial will be as soon as the approval for the study will be obtained. The end point will be the last visit of the last patient enrolled in the trial.

First act of recruitment is the screening:

The recruitment of patients for the investigator-initiated trial takes place during the consultation hours of the study centre. Since patients are specifically assigned for partial meniscus implantation, patients are already informed about the investigator-initiated trial at the time of appointment. During the first visit the inclusion and exclusion criteria are evaluated. If the patient qualifies for participation in the study based on the inclusion and exclusion criteria, he/she will be informed about the therapeutic procedure of partial meniscus implantation with Spongioflex® and the planned investigator-initiated trial (planned visits, data protection, etc.) will be explained. Patients also receive an information sheet explaining the surgical procedure, the advantages and disadvantages, the risks, and the follow-up treatment. After a sufficient reflection period, the patient must sign the consent form for participation in the investigator-initiated trial and the data protection declaration. Without these written consents, inclusion in the investigator-initiated trial cannot take place. After the signatures, the patient is included in the investigator-initiated trial. In accordance with standard clinical practice, the usual risk information for the surgical procedure is provided, for patients who decided to be operated. For the control group (not operated patients) the follow up visits are explained. This is conducted based on the information sheet customary in the respective hospital. In this form, patients are usually informed about the procedure, the treatment alternatives, the risks, and the aftercare. Women are treated in the same way. Spongioflex® does not affect the body's metabolism and does not influence the effect of medications the patient is taking, thus there is no need for special female treatment option. There is no restriction for medication taken by the patient.

Pregnant women are excluded from surgery but can join the non-operated group.

Minor patients are not included.

The investigator-initiated trial may only be terminated prematurely for ethically relevant, i.e., medical/scientific reasons.

Premature exclusion of a patient from the study:

- If, during the waiting period for the Spongioflex® graft, changes in the patient's state of health occur that constitute a contraindication for partial meniscal implantation (e.g., infection of the knee joint, tibial plateau fracture), the physician conducting the study must withdraw the patient from the investigator-initiated trial if this appears reasonable and necessary for medical reasons.

Premature termination of the entire study: Reasons for premature termination of the investigator-initiated trial include:

- If the identifiable risks outweigh the expected benefits.
- If an unreasonable risk to patients is apparent.
- If unexpected serious adverse events (SAE); Suspected Adverse Drug Reaction (SADR) occur that are causally related to the insertion of the meniscal implant, they will be reported to the EudraVigilance database. Patients will be followed up until the SAE or SUSAR/SADR is solved, if necessary, in the hospital, otherwise as outpatient.
- IF SUSARs are reported, a new benefit/risk balance evaluation will be performed and after the analysis it is decided if the study will be continued.

If the investigator-initiated trial is terminated or suspended prematurely, the study director will inform the regulatory authority(ies) of the termination or suspension and provide a statement to that effect. The Ethics Committee will be promptly notified and provided with a detailed written explanation for the study director's termination or suspension of the investigator-initiated trial, as specified in the applicable regulatory requirements. If the investigator-initiated trial is terminated or suspended prematurely for any reason, study participants will be notified immediately.

Patients can stop the participation of the study at any time, without giving the reason for it.

The investigator and the sponsor are the same person, He has the right to decide if there will be an early site closure or if the study will be prematurely terminated. For further details see 10.5 (Early site closure or trial termination) for criteria and responsibilities related to early site closure or trial termination.

In the event of premature termination or suspension of the investigator-initiated trial, irrespective of the reason, further follow-up of patients will continue according to standard clinical practice.

5 TRIAL POPULATION

5.1 Selection of Trial Population

This trial is performed on adult patients with a maximal age of 60 years. The enrollment criteria are carefully selected to increase patient safety and efficacy of the procedure. Patients must have a partial loss of the lateral or medial meniscus and a lateral or medial joint line pain. In this trial there are no drugs used. The human cancellous bone (SUB184038) is used in various dimensions to suite the defect. The progression of this partial loss ist the total loss of the meniscus, which is treated with total meniscal allograft replacement and when the cartilage is severely damaged a TKA is the only treatment option. The patients treated in this trial are mainly young active patients who want to continue their sport and daily life. Thus, to try to improve knee functionality is the goal of the partial meniscal replacement.

5.2 Rationale for Trial Population

The rational for choosing this trial population is that this part of the population has this kind of diagnosis, and it must be treated as soon as possible. Additional measures are taken for leg axis misalignment and ACL rupture. For the efficacy of the procedure the leg must have a normal alignment and must be stable.

No children or patients, who are unable to consent for themselves, or those that may respond to the trial intervention differently are included. There is no restriction on medicine taken by the patient because the allograft does not have systemic actions.

Screening is performed via MRI. There must be a sufficient standing peripheral rim, so that the procedure can be performed. No laboratory tests or genetic tests are necessary for the screening. When the operation is decided later on, the usual laboratory tests are performed as for every surgery, not being a trial. Only after successful screening the patient will be enrolled. Subgroup possible will be sex (female versus male) and smoker versus non-smoker if enough power is generated to do statistical calculations.

Individuals who do not meet criteria for trial eligibility will not be enrolled via protocol waivers. or exemptions.

5.3 Inclusion Criteria

To be eligible to participate in this trial, an individual must meet all the following criteria:

1. Patients (male and female) with:
2. Partial loss of portions of the
 - o lateral meniscus and lateral joint line pain
 - OR
 - o medial meniscus and medial joint line pain
3. sufficient standing of the peripheral rim, so that the procedure can be performed
4. Age: 18-60 years
5. signed written informed consent to the study and to provide the scientific data in pseudonymized form

5.4 Exclusion Criteria

An individual who meets any of the following criteria will be excluded from participation in this trial:

1. The presence of anterior cruciate ligament insufficiency which is not resolved by reconstruction of the anterior cruciate ligament within 16 weeks after partial meniscal implantation.
2. Axial deviation ($>2^\circ$ varus or valgus)
3. realignment osteotomy not performed within 12 weeks

4. advanced cartilage damage (grade III according to ICRS) and osteoarthritis in the affected compartment (grade III according to Kellgren and Lawrence [33])
5. Extension deficit of more than 3° compared to the opposite side or a knee flexion of less than 125°
6. inflammatory arthritis or synovitis on the treated knee
7. BMI greater than 30 kg/m²
8. <18 years, >60 years
9. Chronic pain patients
10. only for patients who will be operated:
 - a. with increased anaesthesiologic risk, e.g., with known or predicted difficult airway
 - b. with increased risk of bleeding
 - c. with increased risk of infection
 - d. with necrotic, infected, or poorly perfused host sides
 - e. history of allergic reactions
 - f. acute hypersensitivity reactions to the IMP or any of its excipients
 - g. pregnant woman

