1.3 Schedule of Activities

Observation parameter in detail:

| Parameter | Screening (EU*) | Enrollment? yes/no | Surgery OP | Follow-up | | | | | |
|---|--------------------|-----------------------|---------------|-----------------|----|----|----|----|----|
| | | | | U1 [#] | U2 | U3 | U4 | U5 | U6 |
| date | V | | V | V | V | V | V | V | V |
| surgeon | V | | V | V | V | V | V | V | V |
| Medical history (age, gender, working status, co-morbidities) | V | | | | | | | | |
| weight | V | | | | | | | | V |
| height | V | | | | | | | | V |
| BMI | V | | | | | | | | V |
| Nicotine | V | | | | | | | | V |
| Side | V | | | | | | | | |
| Previous knee treatment | V | | | | | | | | |
| Cartilage damage | V | | | | | | | | |
| Leg axis misalignment | V | | | | | | | | |
| Properties of the meniscus | V | | | | | | | | |
| Sport | V | | | | | | V | V | V |
| Scores (KOOS, IKDC) | V | | | | | | V | V | V |
| VAS-pain Score | V | | | | | | V | V | V |
| Diagnose | V | | | | | | | | |
| Inclusion criteria | V | V | | | | | | | |
| Exclusion criteria | V | V | | | | | | | |
| Written informed consent | | V | V | V | V | V | V | V | V |
| Pregnancy test | | | V | | | | | | |
| Surgeon | | | V | | | | | | |
| Time of surgery | | | V | | | | | | |
| Graduation after Outerbridge [1] | | | V | | | | | | |
| Way of Fixation | | | V | | | | | | |
| Spongioflex®-properties | | | V | | | | | | |
| Antibiotica | | | V | | | | | | |
| Additional Procedures | | | V | | | | | | |
| Complication | | | V | V | V | V | V | V | V |
| MR-image evaluation | V | | | | V | V | V | V | V |
| Pain at rest | | | | V | V | V | V | V | V |
| Pain when walking | | | | V | V | V | V | V | V |
| Pain at sport | | | | | V | V | V | V | V |
| Pain medication | V | | | V | V | V | V | V | V |
| Reoperation | | | | V | V | V | V | V | V |
| Patient satisfaction | | | | | V | V | V | V | V |

*EU: screening visit; U1: at the end of hospital stay; U2: 6 weeks after surgery (\pm 4 days); U3: 6 months after surgery (\pm 1 months); U4: 12 months after surgery (\pm 1 months), U5: 24 months after surgery (\pm 1 months); U6: 5 years after surgery (\pm 3 months); [#]grey shading: this parameter will only be evaluated when operated

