9.2.1 Statistical Model, Hypothesis, and Method of Analysis

The change in PROMS from baseline in the operated and non-operated group will be compared by two-sided t-test for independent groups when data are normally distributed or with the Mann-Whitney-U-test.

The Null-hypothesis is that partial meniscal replacement does not improve mean PROMs for knee function in comparison to the non-operated group after 2 and 5 years.

The alternative hypothesis is that there that partial meniscal replacement does improve mean PROMs for knee function in comparison to the non-operated group after 2 and 5 years.

The PROMS should improve (Mean KOOS and IKDC should increase by at least 20 points, and VAS-pain score should decrease by at least 3 points, or to near zero, depending on the pre-surgical value).

Analysis of data will be performed by direct comparison of the groups at each time point and in comparison, to before surgery/start of the trial. Mean and standard deviation of the groups are compared. If there is a significant difference, the Null-Hypothesis will be rejected. Even when we have a loss of follow-up of 20% the power will still be 0.985. From our experience mean KOOS values presurgical are between 40-50 and between 50-60 for the IKDC, after treatment the expected improvement is to mean values between 80-90 for both scores. For the VAS-pain-score the presurgical mean value is around 4 and the post-surgical value is between 0 and 1. There is no risk of a type 1 error, because the values are measured several times over the follow-up period, thus there will be no false positive result. If the difference in the scores between pre- and post-surgery is lower than 18, the power is not big enough. Thus setting 20 as the difference for rejecting the Null-hypothesis is supported by enough power, even with only 8/24 patients in the respective group. The covariate could be smoking and sex. Smoking affects healing in general. It is not clear if there will be enough patients in each group to use these as confounders. Interactions will not be possible, because the treatment has no relation to any characteristic of the patient. There will be no adjustment made and no model fitting.

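### Exclusion criterion 1 cannot be settled at enrolment and has no meaning for non-operated patients, and co-surgery is missing from the estimand and the unadjusted comparison

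*Protocol*

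**What the plan says.** **Eligibility.** Protocol 5.4 opens with "An individual who meets any of the following criteria will be excluded from participation in this trial". Criterion 1 is ACL insufficiency "which is not resolved by reconstruction of the anterior cruciate ligament within 16 weeks after partial meniscal implantation". Criterion 2 excludes axial deviation of more than 2° with no condition attached. Criterion 3 reads, in full, "realignment osteotomy not performed within 12 weeks". Only criterion 10 is limited to patients who will be operated, so criteria 1 to 3 formally apply to both groups.

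**When eligibility is settled.** Section 5.2 states "Only after successful screening the patient will be enrolled" and allows no waivers. Section 8.1 has the criteria checked at the first visit, and under 6.6.1 the patient chooses a group after screening. The schedule in 1.3 ticks the exclusion criteria at screening and enrolment only.

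**Who stays in.** Section 5.6 keeps even screen failures in the study. Section 9.2.3 reports all enrolled patients under the full analysis set.

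**Co-surgery.** Section 5.2 says "Additional measures are taken for leg axis misalignment and ACL rupture". Section 2.1 calls for ACL reconstruction at the same time as the implant in one indication. The schedule has an item "Additional Procedures", ticked in the surgery column only.

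**Analysis.** Section 9.2.1 names smoking and sex as possible covariates, and 9.2.5 names age, sex and smoking as possible subgroups. Section 9.2.1 then states "There will be no adjustment made and no model fitting".

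**The concern.** Two linked problems arise.

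First, an entry criterion should be decidable from what is known at entry, and in the same way in both groups. Criterion 1 turns on something that may happen up to 16 weeks after the trial treatment. A patient can receive the implant, miss the window and then meet an exclusion criterion. The protocol gives conflicting answers on what follows. In an open trial whose investigator is also the sponsor, performs all visits and runs the analysis, each such case would be decided with the outcome in view. Each operated patient is 1/30, or 3.3%, of that arm.

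Second, the trial's stated purpose is to evaluate the graft. If some operated patients also have a ligament reconstructed or a leg realigned, and non-operated patients do not, the group difference in KOOS, IKDC and VAS pain measures the whole surgical package. The before-after comparison in the primary endpoint has the same problem. Section 5.2 itself ties efficacy to a stable and normally aligned leg, so the protocol does not treat these operations as neutral to outcome.

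**Working it through.** **Step 1: set the eligibility statements side by side.**

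- ACL timing: 5.4 allows reconstruction up to 16 weeks after implantation, 2.1 says simultaneous, and 2.1 also calls the procedure unsuitable in an unstable knee.
- Time of decision: 5.4 needs information from after surgery, whereas 5.2, 8.1 and the schedule settle eligibility before it.
- Non-operated group: section 6.1 gives it no surgical treatment, so the 16-week period never starts. Read literally, an ACL-insufficient patient can qualify only by choosing surgery.
- Osteotomy: 12 weeks is given without saying from when, or whether before or after implantation. Criterion 2 excludes the malalignment that an osteotomy would correct.
- Consequence of a missed window: 5.4 says excluded, 5.6 and 9.2.3 say kept. Section 7.1.1 does not list it as a reason for discontinuation, and 9.9 and 11.1 say that deviations will not occur, so no rule covers it.

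**Step 2: look for co-surgery in the estimand and analysis.** The treatment attribute in 3.1 is operated or not operated. The intervention in 6.1 is the implant with sutures. The intercurrent events in 9.2.2 are progression to knee replacement, loss to follow-up, death and switching group. Neither ACL reconstruction nor osteotomy appears in any of these, nor among the covariates or subgroups.

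**Step 3: reproduce the protocol's power, to see whether lost numbers are the issue.** Inputs from 9.8: effect size d = 2.0; 30/10 at α = 0.00655, stated power 0.993; 24/8 at α = 0.014, stated power 0.985. Two-sided noncentral t with noncentrality d × √(n₁n₂/(n₁+n₂)):

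- 30/10: 2.0 × √(300/40) = 5.48, 38 df, power 0.9935.
- 24/8: 2.0 × √(192/32) = 4.90, 30 df, power 0.9857.

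Both agree with the protocol. Removing 3, 6 or 9 of the 30 operated patients at α = 0.00655 leaves power of 0.992, 0.989 or 0.984. The issue is bias, not power.

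**Step 4: illustrate the bias.** If a share f of operated patients has co-surgery that adds g points by itself, and no control does, the bias in the group difference is f × g. The protocol gives neither value. Assuming f = 10–50% and g = 10–20 points:

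- lowest: 0.10 × 10 = 1 point, 5% of the 20-point target in 9.2.1;
- highest: 0.50 × 20 = 10 points, 50% of it.

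Section 9.8 expects gains of 84 − 55 = 29 points (IKDC) and 86 − 46 = 40 points (KOOS). Against these, 1 to 10 points is 3–34% and 2.5–25%.

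The SD is not stated. With d = 2.0, a difference of 20, 29 or 40 points implies an SD of 10, 14.5 or 20. If the graft itself did nothing, the chance of p < 0.05 (two-sided t-test, 30/10) would be:

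| SD | bias 1 point | bias 4 points | bias 10 points |
|---|---|---|---|
| 10 | 0.058 | 0.187 | 0.761 |
| 14.5 | 0.054 | 0.114 | 0.453 |
| 20 | 0.052 | 0.083 | 0.266 |

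These figures hold the SD equal in both groups. Mixing patients with and without co-surgery would widen the operated group's spread and lower the larger values.

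**The case against.** The strongest reply is that criterion 1 is only loosely worded. It can be read prospectively, as excluding ACL insufficiency for which no timely reconstruction is foreseen. A reader might infer that the plan removes operated patients after treatment, and the documents do not support that. The exclusion criteria are not rechecked after surgery, and a missed window is no ground for discontinuation in 7.1.1. Withdrawal by the investigator is tied to rehabilitation non-compliance (7.2) or to a contraindication arising while waiting for the graft (4.4, 10.5). The full-analysis-set statements point to keeping such patients. That reply stands: late exclusion is a risk created by conflicting text.

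A reader might also infer that osteotomy is done weeks after implantation. Criterion 3 does not say so, and if criterion 2 holds unconditionally, few or no patients may have an osteotomy.

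It is also fair that supplementary analyses and co-procedure tables are often left to an SAP, which is not shown. But the treatment definition, the list of intercurrent events and the ruling-out of adjustment are fixed in this protocol, and they are what the point rests on.

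Finally, 6.8.2 permits every other therapy, so a non-operated patient could in principle have ligament surgery. Section 6.1 gives that group no surgical treatment, so co-surgery is still expected essentially in one group.

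**Conclusion.** The point holds in two parts. Criterion 1 cannot be decided at enrolment, is undefined for non-operated patients, and conflicts with 2.1, 5.2, 5.6 and 9.2.3; the osteotomy criterion lacks a reference point. Separately, co-surgery is foreseen but has no place in the treatment definition, the intercurrent events or the analysis, so following the plan credits the graft with any gain from it.

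The size of that second effect is unknown. The 1 to 10 points rest entirely on assumed shares and gains and should not be read as an estimate. At the low end the effect is negligible; at the high end it is half the target difference. The comparison is also non-randomised, so removing this source of bias would not remove the others. The point should be corrected, at little cost.

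**What to change.** 1. The sponsor should reconcile 5.4 with 2.1, 5.2, 5.6 and 9.2.3 so that eligibility can be decided at enrolment in both groups, and should give the osteotomy period a reference point and a stated relation to the axial-deviation criterion. Which surgical timing is right is a clinical matter, and no view is offered.
2. State in 9.1 and 9.2.3 that an enrolled patient is not removed from the full analysis set because a later procedure was missed.
3. Record ACL reconstruction and osteotomy by type and date, in both groups and at all visits. The existing items do not do this alone: "Additional Procedures" is ticked only at surgery and the leg axis item only at screening. The Reoperation item, ticked at U1 to U6, can carry later procedures, provided that it is confirmed as collected in both groups.
4. Tabulate co-surgery by group.
5. Pre-specify in 9.2.5 the primary comparison restricted to patients without co-surgery. It stays supplementary, since co-surgery may be decided after enrolment.

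The cost is wording, slightly more detailed data capture and one smaller analysis. With equal SDs, the standard error is proportional to √(1/n₁ + 1/10). Going from 30 to 21 operated patients raises it from 0.365 to 0.384 (5%). Going to 15 raises it to 0.408 (12%).

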3 TRIAL OBJECTIVES, ENDPOINTS AND ESTIMANDS

3.1 Primary Objective + Associated Endpoint and Estimand

| Primary Objective | Primary Endpoint |
|---------------------------------------|--|
| To evaluate efficacy of the procedure | Improvement of PROMs (KOOS, IKDC, VAS Pain Score) 2 and 5 years after surgery compared to scores of the non-operated group and compared to pre-surgery scores. |

Primary Estimand (Variable): Difference in PROMs after 2 and 5 years

Endpoint: 2 and 5 years after surgery/enrollment, or progression to TKA

Treatment: varies with the group chosen by the patient (operated or not operated)

Population: male and female patients between 18 and 60 years

Intercurrent event: progression of osteoarthritis up to TKA, lost to follow up, premature death, the patient wishes to change to the operated group after a certain time (The process: progression of osteoarthritis is very slow. It will be very unlikely that more than 1 patient wants to change to the operated group within the 5 years of the trial. The same is true for progression to TKA. The possibility to change later in the operated group will take off the pressure from the patient to make the “wrong” decision now.)

Population-level summary: The primary objective is to compare the PROM change from baseline between the operated and non-operated group after 2 and 5 years. The difference in obtained PROMS will be evaluated.

Estimand Description: The Estimand are the Difference in PROMs. This includes specific knee scores (IKDC, KOOS) and the VAS-Pain Score. IKDC and KOOS have values between 0 and 100 and the higher they are as better the function of the knee. The VAS Pain Score has values between 0 and 10 and the higher the score the higher the pain.

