4 TRIAL DESIGN

4.1 Description of Trial Design

Description of Intervention Model

This investigator initiated; low intervention trial is performed with 2 groups. The intervention group is the group of patients who will be operated. The control group are the patients not willing to be operated. Due to the incidence of patients with partial meniscal loss in the last years in the private praxis of the principal investigator 30 patients in the operated group and 10 patients in the non-operated group will be recruited within 2 years of recruitment. The study will be performed to prove patient safety and efficacy of the procedure. The process of progression of osteoarthritis is very slow. It will be very unlikely that more than 1 patient will be in this situation and wants to change to the operated group within the 5 years of the trial. The same is true for progression to TKA. The possibility to change later in the operated group will take off the pressure from the patient to make the “wrong” decision now.

Description of Trial Duration

The total trial duration will be 7 years. The recruitment period will be 2 years. Follow-up is 5 years. Depending on, if the patient will be operated or not, the time until surgery will add on these 5 years. The substance used (human cancellous bone) does not have a dose. It will be used in various dimensions.

Method of Assignment to Trial Intervention

This is a single centre trial. The initiator of the trial will perform the trial on its own. Due to the small number of patients included, the investigator will perform all visits on its own. There is no randomization. The patient decides if he/she will be operated or not. There is no blinding. A clinical monitor will perform data monitoring. There are no plans for a data monitoring committee due to the small number of patients and small number of data recorded. Bias is minimized by investigating the MRI images after a standardized protocol. The PROMs are filled in by the patient without the help of the investigator. The analysis will be performed by the investigator using statistical software. Patients from the non-operated group can transition to the operated group at any time. There are no rules for transition.

An interim analysis is planned after 2 years. See details in section 9.7

There will be no sample collection during the trial. In the moment there is no extension of the trial over the 5 years planned.

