6.6 Participant Assignment, Randomisation and Blinding

6.6.1 Participant Assignment

The patient decides after screening on its own if he wants to be operated or not. For this reason, the patient decides to which group he will belong.

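### Criterion 10 excludes only operated patients, so the two groups of the unadjusted primary comparison have different entry criteria

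*Protocol*

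**What the plan says.** Exclusion criteria 1 to 9 in section 5.4 bind every participant. Criterion 10 applies "only for patients who will be operated". Its items are raised anaesthetic risk (a), bleeding risk (b), infection risk (c), a necrotic, infected or poorly perfused host site (d), a history of allergic reactions (e), hypersensitivity to the implant material or its excipients (f) and pregnancy (g).

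Section 4.4 spells out the consequence for item g: "Pregnant women are excluded from surgery but can join the non-operated group".

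The control group is described in terms of preference. Section 4.1 states: "The control group are the patients not willing to be operated". On assignment, the same section says "The patient decides if he/she will be operated or not", and section 6.6.1 says "The patient decides after screening on its own if he wants to be operated or not". Section 4.1 adds "Patients from the non-operated group can transition to the operated group at any time", and says that no rules govern this.

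Section 3.1 sets the use of the control group: "The primary objective is to compare the PROM change from baseline between the operated and non-operated group after 2 and 5 years". Section 9.2.1 specifies an independent two-sided t-test or a Mann-Whitney test, and closes with "There will be no adjustment made and no model fitting".

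**The concern.** A comparison of surgery with no surgery is informative for patients who could have had either. The choice-based definition in section 4.1 points to such a group: candidates for implantation who decline it. Criterion 10 and section 4.4 do not hold to that definition. They leave the control group open to patients who could not have been operated on when they enrolled.

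For those patients the protocol's account of assignment does not fit, because the decision is not theirs while the bar lasts. The open transition to surgery does not fit either. Section 2.2 tells controls that changing group is their means of limiting deterioration, which a control who meets criterion 10 cannot do while the bar lasts.

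This is separate from self-selection. Self-selection can in principle be partly addressed by adjusting for measured baseline differences. A characteristic that entry rules permit in one group and forbid in the other has no overlap at entry, so a model has nothing to compare it with. The entry criteria are the place to repair it.

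**Working it through.** **The passages side by side**

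| Question | Operated group | Non-operated group | Source |
|---|---|---|---|
| Criteria 1 to 9 apply? | Yes | Yes | 5.4 |
| Rim sufficient for the procedure required? | Yes | Yes | 5.3, item 3 |
| Criteria 10a to 10f apply? | Yes | No, by the restriction in criterion 10 | 5.4 |
| Pregnancy excludes? | Yes | No, stated expressly | 5.4 item 10g, 4.4 |
| Who decides the group? | The patient | The patient | 4.1, 6.6.1 |
| Can later have surgery? | Not applicable | At any time, without rules | 4.1 |

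Three things follow.

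1. No section requires a control to be fit for surgery. For pregnancy the admission is explicit. For 10a to 10f it follows from the restricted wording.
2. The asymmetry does not depend on who wanted what. Suppose section 4.1 is read strictly, so that only decliners are controls. A decliner with raised bleeding risk or an allergy history is still eligible, while the same patient choosing surgery is excluded.
3. Section 8.5.1 requires a pregnancy test before a control changes to surgery, while section 4.1 says there are no rules for transition. These passages, and criterion 10, need to be reconciled.

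**Overlap of 10e and 10f.** Item 10e is an unqualified allergy history. On its wording it largely takes in the specific hypersensitivity of 10f, and it widens the set of patients who are eligible only as controls.

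**Weight of one such patient**

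Inputs: 10 controls enrolled and 8 remaining after 20% loss (section 9.8); a 20-point improvement sought in KOOS and IKDC (section 9.2.1).

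The share of the control mean per patient is 1/n:
- n = 10: 1/10 = 10%
- n = 8: 1/8 = 12.5%

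If k of n controls have a mean change that differs by x points from the other controls, the control mean shifts by (k/n) × x. The protocol gives neither k nor x. Taking k = 1 and assuming |x| between 5 and 20 points, with the sign left open:
- n = 10: 5/10 = 0.5 to 20/10 = 2 points, which is 2.5% to 10% of the 20-point target
- n = 8: 5/8 = 0.625 to 20/8 = 2.5 points, which is 3.1% to 12.5% of the target

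This shows only the sensitivity of a small control group; it is not an estimate of bias.

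**The plan's own figures.** For 10 and 30 patients, effect size 2.0 and two-sided α = 0.00655, the noncentral t distribution gives power 0.9935 (section 9.8 states 0.993). For 8 and 24 with α = 0.014 it gives 0.9857 (stated 0.985). Both reproduce. The eligibility point does not depend on them.

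**The case against.** The best defence is that criterion 10 is mostly about the safety of surgery and of the implant, so limiting it to those who have surgery is a recognisable design choice. The main knee-related exclusions (ligament, axis, cartilage and osteoarthritis, range of motion, synovitis) and BMI and chronic pain already bind both groups. Item 10d is the clearest knee-related exception. This limits how much difference the asymmetry is likely to make, but does not remove it.

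A second defence is that self-selection without adjustment dominates the non-comparability and would remain after this change. That is true. It is no reason to add a difference that adjustment could not fully repair.

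Three textual defences are weaker. The opening of section 5.4 excludes anyone meeting any criterion from the trial, but criterion 10 restricts itself and section 4.4 confirms the narrower reading. The withdrawal rule in sections 4.4 and 10.5 covers contraindications that arise while waiting for the graft, not entry as a control. Pregnancy during follow-up can occur in both groups (section 8.5.1), which is why the point is confined to status at entry.

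A practical objection stands in part. Section 5.2 foresees no laboratory tests for screening, and the usual pre-operative tests follow only once surgery is decided. Extending criterion 10 to everyone should not create work-up for decliners.

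A reader might also infer that patients who want surgery but are barred are routed into the control group. The protocol says this only for pregnancy, and without mention of what the woman wanted. For 10a to 10f it is a gap in wording, and section 4.1 can be read against it.

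**Conclusion.** The point holds as a flaw in the entry criteria. The groups of the unadjusted primary comparison are recruited under different rules, and those rules do not fit the choice-based definition of controls or the open transition to surgery. What is certain is the structure, and the weight of 10% to 12.5% of the control mean per such patient.

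The size and direction of the bias are unknown. A reader might infer that it favours the implant, because patients with comorbidity may do worse. The documents do not support a direction. The primary variable is change from baseline, so a baseline temporarily worsened by pregnancy would inflate a control's later improvement and work against the implant.

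A reader might also assume several such controls, each with a large deficit, and conclude that a sizeable part of the 20-point target could come from eligibility alone. Neither input has a source in the protocol. Assuming many such controls would also be hard to square with expecting little recruitment loss when they are excluded. Nor does the flaw by itself make the trial unable to answer its question: the comparison is distorted only to the extent that such controls enter and their outcomes differ.

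**What to change.** Reconcile sections 4.1, 4.4, 5.4 and 6.6.1, with the matching text in 8.1, as follows.

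- Apply the same eligibility criteria to both groups at enrolment, judged from history and information already available at screening and with no new tests. Define controls as patients eligible for implantation who decline it. This extends to medical candidacy what inclusion criterion 3 already asks of everyone anatomically.
- Remove the clause in section 4.4 that admits pregnant women as controls. Re-screening under section 10.3 is already available once an exclusion no longer applies.
- Reconcile items 10e and 10f so that their scopes are distinct.
- Reconcile the statement on transition in section 4.1 with criterion 10 and section 8.5.1.

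If controls who meet criterion 10 are kept, record this at baseline and report the primary comparison without them as well.

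The cost is wording, plus a somewhat smaller pool for the 10 control places in a single practice recruiting over 2 years. The protocol gives no figures from which to estimate the loss. Some asymmetry will remain for conditions that come to light only in the pre-operative work-up, which controls do not have.
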